levels compared to control and high fat diet groups (**Figure 2A-B**). Furthermore, supplementation with GPE led to the increase in irisin plasma level (**Figure 2C**)(11).

In order to understand the underlying mechanism involved in the GPE-related irisin increased levels, we next evaluated the effects of epicatechin, one of the main flavonoids present in GPE, in L6 myotubes challenged with palmitate, to mimic a condition of fatty acids oversupply. Protein levels of PGC- 1 α and FNDC5 were significantly higher in the EC and palmitate-treated cells, compared with palmitate-treated cells (**Figure 3A-B**). The same tendency was observed by immunocytochemical analysis of PGC-1 α , while no differences were observed in FNDC5 fluorescence intensity among treatments (**Figure 3D-E**). In addition, EC induced a 2-fold increase in irisin levels secreted to the medium compared with cells treated with only palmitate (**Figure 3C**). These data strongly indicate that phenolic compounds enhance irisin levels in vitro and in vivo.

These intriguing data allow us to hypothesize that phenolic compounds present in grapes might have a positive effect in human health, specially preventing sarcopenia in elderly humans, in part, by increasing irisin levels.

4) Enrollment Numbers

We chose the “changes in plasma irisin levels” as our primary outcome to determine the power calculations for sample size. Based on our preliminary data (11), 5 individuals per group are required to reach 80% power to detect differences in irisin levels between the groups, at a $\alpha=0.05$, using a two-sided paired T-test. We propose to enroll 7 individuals per group, instead of 5, in the event of a patient drop out of the study (for any unforeseen circumstances). In total we will have 14 subjects.

5) Inclusion and Exclusion Criteria

Inclusion Criteria: postmenopausal women aged 60 years or older with a hand-grip strength media value of 16 kg or lower, normal body mass index (BMI) with values between 18.4 and 24.9 kg/m², blood pressure below 130/80 mmHg, and plasma glucose and cholesterol concentrations below 100 and 200 mg/dl.

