Exclusion Criteria: history of specific muscle diseases, peripheral vascular disease, intermittent claudication, central and peripheral nervous system disorders, cachexia, active diagnosis of diabetes mellitus, myocardial infarction, stroke, liver disease, on dialysis or long-term steroid therapy, and/or actively receiving treatment for cancer or severe infection (excluding short-term antibiotic therapy), weight less than 140 pounds, anemia and blood donations in the past 30 days. In addition, participants should not be taking dietary supplements at the time of the study.

6) Recruitment Methods

We will recruit by: 1) posting flyers on campus bulletin boards; 2) listing the study on our departmental website that provides a list of all current departmental trials; 3) listing the study on campus list servers; 4) advertising in the local newspapers and 5) posting on social media. All recruitment material will use similar language and list a study office phone number, clinical coordinator email and the departmental website for clinical trials (**Attachment A**). Respondents will be contacted by phone and pre-screened. Information about the study will be provided during the phone interview (**Attachment B**). For subjects that are eligible and interested in enrolling in the study, an in-person screening visit 1 appointment will be scheduled with the investigator or designee and the informed consent form emailed to them in advance. If the participants meet all the inclusion criteria, in the same visit the investigator or designee will review the informed consent form with the subjects, explain the study to the subjects and answer any questions prior signing the consent. Only once the informed consent form is signed, a diet history questionnaire (**Attachment C**) will be completed by the subjects.

7) Compensation to the Subjects

Subjects will be compensated at a rate roughly proportional to the inconvenience

incurred according to the following schedule:

- Visit 0 (screening): \$50 for inconvenience
- Visit 1: \$75 for inconvenience
- Visit 2: \$75 for inconvenience
- Visit 3: \$75 for inconvenience + \$50 for study completion

Subjects will be paid at the completion of their involvement in the study. The total compensation that a participant might earn is \$325 for completion of all visits. Subjects that withdraw from the study early will be compensated based on the visit(s) they completed.

8) Screening procedures to determine eligibility:

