Return stool and urine collection kit			X	X
Adverse events assessment			X	X

After confirmation of the inclusion/exclusion criteria enrolled subjects will be asked to travel to Ragle Human Nutrition Center at University of California Davis for 3 study visits: a baseline visit (**visit 1**), and a 3-week intervention visit (**visit 2**) and a final 6-week visit (**visit 3**)

Visit 1 (baseline visit):

On this visit, baseline measurement will be done. Fasted participants (12 h) will provide blood samples and complete two tests:

Blood samples: from each participant 20 ml of blood will be extracted. The following parameters will be measured in plasma, (the same parameters will be measure in the following visits 2 and 3):

Blood parameter	Volume of blood needed	Visit 1	Visit 2	Visit 3
Irisin	1200 ul	X	X	X
Glucose	1000 ul	X	X	X
Insulin	1200 ul	X	X	X
GLP-1/ 2, GIP	2000 ul	X	X	X
Adiponectin, leptin and ghrelin	3000 ul	X	X	X
Blood urea nitrogen, creatinine	1000 ul	X	X	X
Total cholesterol, triglyceride, high-density lipoprotein (HDL), low-density lipoprotein	2000 ul	X	X	X
Aspartate transaminase, Alanine transaminase	2000 ul	X	X	X
IL-6, IL-15	2000 ul	X	X	X
25-hydroxyvitamin D	1000 ul	X	X	X
Hematocrit	500 ul	X	X	X

Total volume of blood per visit	~ 20 ml	20 ml	20 ml	20 ml
---------------------------------	---------	-------	-------	-------

After taking the blood samples a snack will be provided to the participants in order to complete the following tests.

1. Hand-grip strength: previously described in the screening point
2. Short Physical Performance Battery (SPPB): the SPPB score will be based on three tests, as follows: balance test, gait speed test, and chair stand test (see **Attachment E**). Of note, these tests have been used as a predictive tool for possible disability and can aid in the monitoring of function in older people.

Following, the subjects will randomize into the study supplement: a) Placebo powder (46 g placebo powder in 180 ml of water); or b) freeze-dried table grape powder (46 g grape powder in 180 ml of water). The supplement will be supplied to the participants to complete the following 3 weeks supplementation until the next visit. The investigator or designee will explain the details regarding the preparation and consumption of the supplement [a dosing protocol will be uploaded too (**Attachment F**)].

Also a 24-hs food and physical activity questionnaire will be performed

Briefly, at visit 1:

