- Subjects will arrive fasted for at least 12 h prior to this visit (water ok).
- A finger stick blood sample will be collected (to confirm fasting).
- Concomitant medications and accomplishment of inclusion and exclusion criteria will be reviewed.
- 24-hs food and physical activity questionnaire
- Seated resting blood will be measured.
- Weight will be measured.
- Venous blood samples will be collected for analytical determinations (20 ml).
- A hematocrit will be performed in order to discard anemia.
- Snack ingestion
- Hand grip strength and SPPB test will be completed.

- The supplement will be provided to the subjects for a 3 weeks supplementation period.
- Stool and urine collection kit and a standardized log and instructions (**Attachment G and H**) will be provided to subjects. The kits will be returned at visit 2.

Visit 2 (3-weeks visit):

Subjects will return to the Ragle Facility for the follow-up visit. This visit will take approximately 2 h to complete.

Briefly, at visit 2:

- Subjects will arrive fasted for at least 12 h prior to this visit (water ok).
- Subjects will provide fecal and urine samples collected with the collection kit.
- A finger stick blood sample will be collected (~1 drop).
- Concomitant medications and accomplishing of inclusion and exclusion criteria will be reviewed.
- 24-hs food and physical activity questionnaire
- Seated resting blood pressure will be measured.
- Weight will be measured.
- Subjects will take the assigned supplement.
- Venous blood samples will be collected (20 ml).
- A hematocrit will be performed in order to discard anemia.
- Snack will be provided to the participants.
- Hand grip strength and SPPB test will be completed.
- Enough supplement will be provided to the subjects for a 3 weeks supplementation period.
- Unused and empty packages of the study product will be return.
- Stool and urine collection kit will be provided to subjects. The kits will be returned at visit 3.

Visit 3 (final visit):

Subjects will return to the Ragle Facility for the final visit. This visit will also take approximately 2 h to complete.

Briefly, at visit 3:

- Subjects will arrive fasted for at least 12 h prior to this visit (water ok).
- Subjects will provide fecal and urine samples collected with the collection kit.
- A finger stick blood sample will be collected (~1 drop).
- Concomitant medications and accomplishing of inclusion and exclusion criteria will be reviewed.

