Data confidentiality: After obtaining written informed consent, all subjects will be assigned an identification number (ID) and all data and specimens will be collected from individuals and stored using this ID number. The key linking the subjects' personal information to their laboratory results will be kept in a locked drawer in the investigator's office. Only authorized research personnel will have access to the study data. People outside the research process will not have access to results about any one person. Staff analyzing the data will only have access samples identified by subjects' ID number. The subjects'

personal information (questionnaires and consent form) will be kept separately under lock and key in the investigator's office

13) Withdrawal of Subjects

Possible reasons for removal include specific muscle diseases, peripheral vascular disease, intermittent claudication, central and peripheral nervous system disorders, cachexia, active diagnosis of diabetes mellitus, myocardial infarction, stroke, liver disease, on dialysis or long-term steroid therapy, and/or actively receiving treatment for cancer or severe infection (excluding short-term antibiotic therapy) that are diagnosed ones the subject are already enrolled in the study. If the participants start taking supplements. Also, if the participants experiment a remarkable increment in body weight, blood pressure and plasma glucose and cholesterol concentrations above 100 and 200 mg/dl. Finally, development of anemia during the study will be another reason for removal.

14) Risks to Subjects

Venipuncture: Risks of venipuncture include some discomfort, bruising, and rarely, infection. Blood collections will be performed by a registered nurse to minimize discomfort.

Blood volume: The amount of blood to be drawn during the study will be ~60 mL, collected over a period of 6-weeks. We will take a finger stick blood sample (~1 drop, equal to ~100 ul) at visits 0, 1, 2 and 3 and 20 mL/visit at visits 1, 2 and 3. These volumes are well within the recommended allocated volume for healthy adults. Nevertheless, the patients could experiment dizziness, nausea and physical weakness.

Study products: The components of the dietary supplement and placebo are detailed in **Attachment I** and **Attachment J**, respectively. The dose that the participant will consume daily is the equivalent to a ~150 g (1.5 cups) of fresh grapes, which won't represent a health risk for the participant

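### Section 13 lets a randomised woman be removed for starting a supplement or for a new listed diagnosis without separating stopping product from leaving follow-up, so her week-6 outcomes are not planned for

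*Protocol*

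**What the plan says.** Section 5 bars supplements during the trial: "In addition, participants should not be taking dietary supplements at the time of the study".

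Section 13 opens its list with "Possible reasons for removal include specific muscle diseases, peripheral vascular disease, intermittent claudication". It continues with other conditions, including stroke and myocardial infarction, limited to those "that are diagnosed ones the subject are already enrolled in the study". It then adds "If the participants start taking supplements". The only outcome it names is removal.

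Section 9 places grip strength, SPPB and the blood draws at fixed visits, and schedules "Adverse events assessment" at visits 2 and 3 only. The procedure lists for those two visits also state: "Concomitant medications and accomplishing of inclusion and exclusion criteria will be reviewed". That review is listed before the venous blood draw and the grip and SPPB tests.

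Section 7 pays by visit and states: "Subjects that withdraw from the study early will be compensated based on the visit(s) they completed". The completion amount comes with visit 3.

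Section 4 makes the only provision for loss: "We propose to enroll 7 individuals per group, instead of 5, in the event of a patient drop out of the study". It describes this as cover for circumstances that cannot be foreseen.

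**The concern.** A woman can stop the study product, or break the supplement restriction, and still have her grip strength and irisin measured at week 6. Section 13 does not allow for this: the one step it describes takes her out of the study.

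The triggers arise after randomisation. A woman may start a supplement because she feels weak or perceives no benefit, so removal could be related to prognosis and possibly to arm. The protocol does not say who among those eligible for removal is actually removed, which opens a second route to selective loss. The week-6 comparison would then rest on women who stayed on plan rather than on all those randomised. The direction of any bias cannot be told from the document.

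An analysis plan cannot repair this. It can define analysis sets and handle missing values, but it cannot recover a measurement that was never taken.

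A second issue follows from pay. If removal ends payment, a woman who reports a supplement may lose money that a silent woman keeps. That would work against detecting the contamination the rule is aimed at.

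**Working it through.** **1. The sections side by side**

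| Question | Where | Answer in the protocol |
|---|---|---|
| What may happen after a supplement start or new listed diagnosis? | Section 13 | Removal from the study (possible, not automatic) |
| Is stopping product distinguished from leaving follow-up? | Sections 9, 13 | No |
| When are week-6 outcomes taken? | Section 9 | Visit 3 only |
| When are adverse events assessed? | Section 9 schedule | Visits 2 and 3 |
| Is any visit planned after removal? | Sections 9, 13, 17 | None; Section 17 names only completion or early withdrawal |

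So a woman removed before visit 3 has no planned week-6 assessment of any kind.

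**2. Share of an arm lost**

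With 7 per arm (Section 4), one removal is 1/7 = 14.3% and two are 2/7 = 28.6%.

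**3. Pay (Section 7)**

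Stated total reproduced: 50 + 75 + 75 + 75 + 50 = $325.

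| Removed | Paid | Forfeited |
|---|---|---|
| After a completed, paid visit 2 | 50 + 75 + 75 = $200 | 325 − 200 = $125 (38%) |
| Between visits 1 and 2 | 50 + 75 = $125 | 325 − 125 = $200 (62%) |

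Both rows assume that the rule for women who withdraw also applies to women who are removed. The first row further assumes that a woman who discloses at visit 2 still completes that visit. The protocol does not settle this, because the criteria review is listed before the blood draw and tests.

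**4. Numbers and power, as a side check**

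The figure of 5 per group cannot be reproduced, because the protocol gives no effect size or SD. Solving backwards with the noncentral t for n = 5, power 0.80 and two-sided α = 0.05 gives an implied standardised effect of 2.02 for two independent groups, or 1.68 for the paired test that Section 4 names. At those assumed effects:

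| Women left per arm | Power, independent groups | Power, paired |
|---|---|---|
| 7 | 0.93 | 0.96 |
| 6 | 0.88 | 0.90 |
| 5 | 0.80 | 0.80 |
| 4 | 0.67 | 0.62 |

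The allowance covers 7 − 5 = 2 losses per arm. The protocol gives no loss rate, so a range is assumed. With per-woman probability of loss p and X ~ Binomial(7, p), the chance that at least one arm falls below 5 is 1 − (1 − P(X ≥ 3))²:

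| Assumed p | P(X ≥ 3), one arm | At least one arm below 5 |
|---|---|---|
| 5% | 0.0038 | 0.7% |
| 10% | 0.0257 | 5.1% |
| 20% | 0.1480 | 27% |
| 30% | 0.3529 | 58% |

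At low loss rates, power is therefore the lesser issue. None of these figures measures selection, which spare women do not prevent.

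**The case against.** Several counter-arguments are sound and limit the point.

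- **Removal is not mandatory.** A reader might infer that every woman who starts a supplement is removed. Section 13 lists possible reasons only. This stands, but discretion without a stated rule does not remove the risk of selective loss.
- **Section 4 shows no intent to discard removed women.** A reader might take the two spare women per arm as evidence that removals are meant to be absorbed. The text ties them to unforeseen drop-out and never mentions removal.
- **The penalty on disclosure is an inference.** Section 7 speaks of women who withdraw, and pay per completed visit is an ordinary arrangement. Nothing shown tells participants that reporting a supplement ends their pay. Disclosure at visit 3 need cost nothing if that visit is completed.
- **Some listed diagnoses may prevent testing.** Stroke or myocardial infarction can make grip or SPPB testing impossible or inappropriate. Continued visits cannot be asked of every woman with a new diagnosis.
- **Adverse events after removal.** That they would go unrecorded is more than the text supports. It shows only that no scheduled assessment remains.
- **Analysis sets may be in the SAP.** The protocol defines no completer set and does not discard data from visits 1 and 2. This stands for the analysis, but not for whether visit 3 takes place.
- **Frequency is unknown.** Supplement starts and new diagnoses over about six weeks may be few, and their link with treatment is plausible rather than documented.

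**Conclusion.** The point holds in a limited form. Section 13 permits removal for two kinds of post-randomisation event, and the protocol plans no assessment afterwards. A woman removed before visit 3 therefore has no planned week-6 grip, SPPB, irisin or adverse-event assessment.

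The main risk is selective loss, at 14% of an arm per removal. Its direction and frequency are unknown. Loss of power is secondary while no more than two women per arm are lost, and the power figures rest on an effect size inferred from n = 5.

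The possible disincentive to report supplements, worth $125 to $200 of $325, depends on reading the withdrawal pay rule as covering removed women. It should be presented as a conditional concern and not as something the protocol states. Whether product should be stopped after any of these events is a clinical matter and is not judged here. For a 14-woman pilot this is a worthwhile, low-cost clarification.

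**What to change.** **Section 13.**
- Separate stopping study product from leaving the study. Leave any decision on product, and on whether assessments are safe, to the investigator.
- State that a woman who starts a supplement, or who has a new diagnosis and whom the investigator judges able to be assessed, is invited to the remaining scheduled visits unless she withdraws consent.
- Record the supplement and its start date.
- Keep her data in her randomised arm, with an on-product analysis as supportive. If the SAP already says this, a cross-reference is enough.

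**Section 7.** State that attended visits and the completion amount are paid whether or not the woman is still taking product. Match the consent wording.

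**Cost.** Protocol and consent wording, plus at most $125 to $200 per affected woman, which is already budgeted for completers. The statistical downside is some dilution of the effect, because a few women will be off product or on another supplement; the supportive analysis addresses that.

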- The person in charge of the test will read grip strength in kilograms from the outside dial and record the result to the nearest 1 kg on the data entry form.
- The person in charge of the test will ask the participant to repeat measurement in the left hand.
- The participant will be asked to repeat two further measurements for each hand alternating sides to give three readings in total for each side.
- The best of the 3 grip strength measurements will be used in statistical analyses to encourage the subjects to get as high a score as possible.
- The person in charge will also record hand dominance, i.e. right, left or ambidextrous (people who can genuinely write with both hands).

For those participants that meet the previous inclusion criteria the following parameters will be explored:

1. Seated resting blood pressure.
2. Weight and height.

3. A finger stick blood sample (~1-2 drop equal to ~ 100ul) will be collected to confirm that subjects meet the inclusion criteria for fasting levels of blood glucose and cholesterol, plus a hematocrit to discard anemia.

Briefly, at Visit 0 (screening visit):

- Subjects will arrive fasted for at least 12 h prior to this visit (water ok).
- Informed consent will be obtained.
- ID number will be assigned.
- Hand grip strength test will be conduct.
- Seated resting blood pressure will be measured.
- Weight and height will be measured.
- A finger stick blood sample (~1-2 drop equal to ~ 100ul) to confirm that subjects meet the inclusion criteria (glucose, cholesterol and hematocrit).
- Diet history questionnaire (**Attachment C**) will be completed by the subjects to review medical history (including known positivity test for COVID-19), concomitant medications (including COVID-19 immunization dates), inclusion and exclusion criteria.
- This visit will take approximately 2 h to complete

9) Procedures Involved

Schedule of procedures

	Visit 0 Screening	Visit 1 Baseline	Visit 2 3-weeks visit	Visit 3 6-weeks final visit
Informed consent	X			
Inclusion / Exclusion criteria	X			
Review medical history	X			
Review concomitant medications	X		X	
Height, weight and blood pressure	X	X	X	X
Finger stick		X	X	X
Hand grip strength test	X	X	X	X
SPPB test		X	X	X

Blood draws for plasma determinations	X	X	X	X
Hematocrit	X	X	X	X
Study product randomization		X		
Study product intake			X	X
Dispense study product for home		X	X	
Return unused study product and empty packages			X	X
Dispense stool and urine collection kit		X	X	

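### Section 13 lets a randomised woman be removed for an undefined rise that includes two secondary endpoints, and provides no visits after removal, so some visit 3 data can be lost needlessly

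*Protocol*

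**What the plan says.** Section 13 of the protocol opens with "Possible reasons for removal include specific muscle diseases" and continues through new diagnoses, starting supplements and anaemia. Within that list it names "a remarkable increment in body weight, blood pressure and plasma glucose and cholesterol concentrations above 100 and 200 mg/dl". The list is permissive: it gives reasons for which a woman may be removed, not an automatic rule.

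The two laboratory values are the entry limits. Section 5 requires "plasma glucose and cholesterol concentrations below 100 and 200 mg/dl". Section 11 lists glucose and total cholesterol among the secondary endpoints, and the blood table in Section 9 schedules both at visits 1, 2 and 3.

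On the checks themselves:
- Visit 0 (Section 8) uses a finger stick "to confirm that subjects meet the inclusion criteria (glucose, cholesterol and hematocrit").
- Visit 1 (Section 9) states "A finger stick blood sample will be collected (to confirm fasting"), and also that "accomplishment of inclusion and exclusion criteria will be reviewed".
- Visit 2 repeats the criteria review and states "A finger stick blood sample will be collected (~1 drop"), without naming the analytes.
- The schedule table ticks the inclusion and exclusion criteria at screening only.

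For women who leave early, Section 7 provides payment for completed visits and Section 17 the return of blood results. No later visit or measurement is described. Section 4 sets the allowance for losses: "We propose to enroll 7 individuals per group, instead of 5, in the event of a patient drop out of the study".

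**The concern.** The clause ties staying in the study to variables that the study measures as outcomes. A woman who enters just under a limit can cross it at week 3 through ordinary within-woman variation. If she is then removed, and removal means no further visits, her week-6 grip strength, irisin and metabolic values are never collected. An analysis plan can say how to handle missing values, but it cannot supply a visit that was not held. This is therefore a matter for the protocol.

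Two things are at stake. The first is information: the trial has 14 women and two spare per arm. The second is that, if the powder changes glucose or cholesterol, the arms would lose different women. A trigger first seen at visit 3 costs little, so the loss arises at visit 2.

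**Working it through.** **Inputs from the protocol.** Limits of 100 and 200 mg/dl (Sections 5 and 13); visits at 0, 3 and 6 weeks (Section 10); 5 per group for 80% power at two-sided 0.05, with 7 per group enrolled and 14 in total (Section 4).

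**The plan's own figure.** Section 4 gives no effect size or SD for irisin, so 5 per group cannot be reproduced forwards. Solving the noncentral t backwards for 80% power at 5 per group gives a standardised effect of 1.68 for the paired test the protocol names, or 2.02 for a two-sample test. I use 2.02, because the two arms contain different women. Power is then 93% at 7 v 7, 82% at 7 v 4, 80% at 5 v 5 and 67% at 4 v 4.

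**Assumptions (the protocol gives no means or SDs), low/middle/high.**
- Glucose: mean 88/92/95, between-woman SD 7, within-woman SD 4/5/6 mg/dl.
- Cholesterol: mean 180/195/210, between-woman SD 30, within-woman SD 10/12/15 mg/dl.
- The analytes are independent and the powder has no effect on either.
- Where a rise over visit 1 is required, I take at least 10 mg/dl for glucose and 20 mg/dl for cholesterol. These cut-offs are mine.

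**Method.** Simulate each woman's true values and keep her if her screening values are under both limits. Add independent noise at each later visit, require visit 1 to be under the limits too, and count those meeting the clause at visit 2. Expected number = 14 × p.

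| Reading of the clause | p, low/middle/high | Women of 14 |
|---|---|---|
| Rise above the limit in both analytes | 0.01/0.1/0.7% | at most 0.1 |
| Above the limit in both, no rise needed | 0.1/0.6/2.2% | at most 0.3 |
| Rise above the limit in either analyte | 2/7/16% | 0.3/1.0/2.3 |
| Above the limit in either, no rise needed | 7/16/27% | 1.0/2.2/3.8 |

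Requiring weight and blood pressure to rise as well would lower the first two rows further.

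**Effect on numbers and power.** The chance that an arm loses more than its two spare women is q = P(Binomial(7, p) > 2), and for at least one arm it is 1 − (1 − q)². This gives 0.1/2/17% if a rise in either analyte is needed and 2/16/50% on the limit alone. Averaging power over Binomial(7, 1 − p) women kept in each arm, from 93% with no loss, gives 93/91/86% and 91/86/78% respectively.

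**Bias.** With no effect of the powder on the analyte, both arms lose the same kind of women and there is none. Now suppose a constant effect at visits 2 and 3 of +5 mg/dl on glucose or +10 mg/dl on cholesterol (assumed, not shown by the protocol). The visit 3 difference among women remaining is:
- Limit alone: glucose 3.7 to 4.3 of 5 as a raw level and 4.8 to 4.9 as change from baseline; cholesterol 6.7 to 7.8 of 10 and 9.3 to 9.8.
- Rise needed, with or without the visit 1 limits: glucose 4.4 to 4.7 and 4.4 to 4.9; cholesterol 8.0 to 8.7 and 8.9 to 9.6.

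Change from baseline thus keeps roughly nine tenths or more of the effect.

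**The case against.** The strongest reply is that the clause, read naturally, bites rarely. It asks for a rise that is remarkable, joins its items with *and*, and only permits removal. If all the rises must coincide, almost no one meets it. If a rise in either analyte is enough, the middle case is one woman of 14, and average power moves from 93% to 91%. Section 4 already allows for losses. The means, SDs and cut-offs are assumed, and the irisin effect is back-solved. All of this stands and limits the point to a minor one. It does not remove it, because under every reading removal can turn on a post-randomisation outcome and no later visit is provided.

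A reader might go further in three ways that the documents do not support.
- **That any value over 100 or over 200 mg/dl means removal.** The text neither makes removal automatic nor clearly drops the need for a rise. Without the visit 1 limits, the limit-alone reading would give 12/24/39%, or 1.6/3.3/5.5 women. However, the visit 1 text says the entry criteria are reviewed, even though its finger stick is described only as a fasting check and the schedule ticks the criteria at screening alone.
- **That the grip strength or irisin comparison is biased.** That would need the powder to shift glucose or cholesterol, which is not shown. The expected harm to those endpoints is fewer women.
- **That visit 2 cholesterol arrives too late to act on.** Only visit 0 names cholesterol on the finger stick, but venous cholesterol is drawn at visit 2, three weeks before visit 3.

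**Conclusion.** The point holds as a cheap improvement. Section 13 permits removal on an undefined rise that includes two secondary endpoints at their entry limits. It does not distinguish stopping the product from leaving the study, and the protocol describes no visits after removal. The consequence is avoidable loss of visit 3 data, ranging from near zero to about 2 of 14 women (1 to 4) across the readings in the table. About 1 (0.3 to 2.3) is the figure if a rise in either analyte is enough. These are upper figures within the assumed means, SDs, independence and cut-offs, because the investigator need not act on the clause. Bias in glucose or cholesterol is a secondary matter and arises only if the powder moves them. Even three women lost from one arm alone would leave about 82% power at the implied irisin effect.

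**What to change.** Reword Section 13 as follows.

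1. The laboratory limits lead to referral, or to stopping the product at the investigator's judgement, and not to leaving the study.
2. The same applies to the other listed reasons (new diagnoses, supplements, weight, blood pressure, anaemia) where it is safe and the woman consents. The missing follow-up affects them equally.
3. Such women attend visits 2 and 3 as scheduled and are analysed in the arm to which they were randomised.
4. Define the remarkable rise as a rise over visit 1, with its size set by the investigator on clinical grounds, and state whether one rise is enough or several must occur together.

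The cost is protocol wording. No visit or sample is added, because visits 2 and 3 are already scheduled. The small downside is that some women analysed will have stopped the product early.
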